#### LTE:

- Obtain long-term data on efficacy (durability) of CLTX-305 (encaleret) on blood calcium concentrations
- Evaluate the long-term PD effects of CLTX-305 (encaleret) on associated measures of mineral homeostasis including iPTH, 1,25-(OH)2 Vitamin D levels and urinary calcium excretion
- Evaluate the long-term PD effects of CLTX-305 (encaleret) on bone turnover markers including C-telopeptide (CTx) and procollagen type 1 N-propeptide (P1NP)

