Abbreviations: Adverse Event = AE; Albumin = Alb; Alanine aminotransferase = ALT; Blood urea nitrogen = BUN; Aspartate aminotransferase = AST; Alkaline Phosphatase = Alk Phos; Electrocardiogram = ECG; BID = Twice daily; Blood Pressure = BP; Calcium = Ca; Calcium Sensing Receptor = CaSR; Chloride = Cl; Concomitant medication = Con. meds; Creatine Kinase = CK; Creatinine = Cr; C-telopeptide = CTX; Dual-energy X-ray Absorptiometry = DXA; Early Termination = (ET); End of Treatment = EoT; Follow-up = FU; Follicle-Stimulating Hormone = FSH; Glucose = Glu; Heart Rate = HR; Hematocrit = Hct; Hemoglobin = Hgb; Lactate Dehydrogenase = LDH; Intact

Parathyroid Hormone = iPTH; Magnesium = Mg; National Institute of Health Clinical Center = NIH CC; Parathyroid Hormone = PTH; Phosphate = PO4; Phosphorus = P; Potassium = K; Pharmacodynamic = PD; Pharmacokinetic = PK; Procollagen type 1 N-propeptide = P1NP; Prothrombin Time/ Prothrombin Time = PT/INR; Red Blood Cell Count = RBC; Thromboplastin Time = PTT; Serious Adverse Event = SAE; QD = Once daily; Total Bilirubin = Tbili; Triglycerides = TGL; White Blood Count = WBC; Women Of Child Bearing Potential = WOCBP

- If participant discontinues from the study early (ET) or withdraws from taking CLTX-305 (encaleret) (EoT), before completing LTE per protocol, participant will be asked to return to the NIH CC within 30 days following the last dose for the ET/EoT visit assessments and return the unused CLTX-305 (encaleret). Participant should resume oral calcium and active vitamin D under the supervision of the study team while the encaleret is being safely discontinued. Follow-up labs should beperformed per this Schedule of Assessments.
- Participants who withdraw from taking CLTX-305 (encaleret) (EoT) before transitioning to the CLTX-305-302/CALIBRATE LTE per protocol will obtain the following outpatient laboratory assessments after the last dose of CLTX-305 (encaleret) and after re-starting their prior regimen of oral calcium and active vitamin D: blood Cr, Ca, Alb, Mg, iPTH, PO4. Follow-up (FU) call should occur within 3-5 days to review the lab results and receive guidance on clinical management of their ADH1 as participants transition to prior standard of care.
-  Unscheduled visits: For laboratory evaluation following dose adjustment or assessment or follow-up of an AE, in which clinically indicated procedures will be performed

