- Document current CLTX-305 (encaleret) dose and calcium dosing regimen, any modifications, and reason for modifications
- Outpatient laboratory testing: Blood samples for clinical laboratory panels (Na, Cl, bicarbonate, K, BUN, Cr and including Alb, Ca, Mg, PO4, iPTH, CTX, and P1NP).
-  Height measured only at month 24/final visit or ET visit
- Vital signs include supine or sitting blood pressure (BP) by automated cuff, heart rate (HR), and respiratory rate.
- Safety and Drug Monitoring Labs collected at the NIH CC visits approximately 4 hours after the morning encaleret dose Chemistry (Na, K, Cl, bicarbonate, Glu, BUN, Cr, Alb, total protein, Ca, Mg, PO4, iPTH, 25-OH Vitamin D, CTX, P1NP, Cholesterol, TG, AST, ALT, Tbili, Alk phos, LDH, amylase, lipase, uric acid, CK), Hematology (RBC, Hgb, Hct, RBC indices, WBC, diff), Coagulation (PT/PTT/INR), Research labs (FGF23 and mid-molecule PTH). HIV, viral hepatitis panel should be repeated within 3 months prior to transition to CLTX-305-302/CALIBRATE.
- 9 Blood β-HCG pregnancy test can be performed at the NIH CC on the day of transition to CLTX-305-302/CALIBRATE Phase 3 LTE, and an aliquot will also be sent to the central lab for the CLTX-305-302/CALIBRATE Phase 3 LTE.
-  CLTX-305 (encaleret) administered and recorded during the NIH CC visit/in-house days.
- Outpatient 24-hr urine collection for Ca, Mg, PO4, Cr, Na, K, citrate, pH
- A final follow-up safety telephone call and outpatient labs will occur 30 ± 7 days after the last dose of CLTX-305 (encaleret).
- 13 If a participant is not able to enter the LTE immediately following Period 3, then participant will be reconsented to and may restart CLTX-305 (encaleret) at the previous therapeutic dose determined in Period 3. Safety and Drug Monitoring Laboratory tests should be done while participant is at the NIH CC.
- When participant transitions to CLTX-305-302/CALIBRATE Phase 3 LTE, participant will be asked to return to the NIH CC to return the unused CLTX-305 (encaleret), and complete any remaining eligibility assessments for the CLTX-305-302/CALIBRATE Phase 3 LTE study.
- 15 If the Month 24 visit aligns with the transition to the CLTX-305-302/CALIBRATE Phase 3 LTE, then the renal ultrasound and DXA scan will be performed once as part of the CLTX-305-302/CALIBRATE Phase 3 LTE.

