# Periods 1, 2, and 3:

Pharmacodynamic endpoints measured over time up to 24 weeks (final visit):

- Blood calcium Absolute levels and change from baseline in cCa
- Urinary calcium clearance (fractional excretion and 24-hour total excretion)
- Renal function (eGFR)
- Serum levels of 1,25-(OH)2 Vitamin
- Blood samples for magnesium, phosphate, creatinine
- Urine samples for pH, magnesium, phosphate, sodium, potassium, creatinine, cAMP, citrate

	
 
Bone resorption markers collagen cross-linked C-telopeptide (CTx)
 
Bone formation markers – blood procollagen type 1 N-propeptide (P1NP)
 

Evaluate the PK of both single and multiple ascending doses of CLTX-305 (encaleret) in participants with ADH1.	
 
PK parameters: maximum plasma concentration (Cmax), time to maximum plasma concentration (tmax), apparent terminal half-life (t½), area under the concentration-time curve (AUC) from time 0 to the last measurable time point (AUC(0-t)), AUC from time 0 to 24 hours (AUC(0-24)), AUC extrapolated to infinity (AUC(0-inf)) following single-doses.
 
Determination of the steady state PK parameters: Cmax, trough concentration (Ctrough), and AUC over the dosing interval AUC(0-tau)
 

 
Obtain long-term data on efficacy (durability) of CLTX-305 (encaleret) on blood calcium concentrations
 
Evaluate the long-term PD effects of CLTX-305 (encaleret) on associated measures of mineral homeostasis including, iPTH, 1,25-(OH)2 Vitamin D levels and urinary calcium excretion
 
Evaluate the long-term PD effects of CLTX-305 (encaleret) on bone turnover markers including C-telopeptide (CTx) and procollagen type 1 N-propeptide (P1NP)
 
	
 
Blood calcium - Absolute levels and change from baseline in cCa
 
Urinary calcium clearance (fractional excretion and 24-hour total excretion)
 
Blood levels of iPTH
 
Renal function (eGFR)
 
Serum levels of 1,25-(OH)2 Vitamin D
 
Blood samples for magnesium, phosphate, creatinine
 
Urine samples for pH, magnesium, phosphate, sodium, potassium, creatinine, cAMP, citrate
 
Bone resorption markers collagen cross-linked C-telopeptide (CTx)
 
Bone formation markers – blood procollagen type 1 N-propeptide (P1NP)
 

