7.0 Study Objectives

This study is a single-site, open-label, dose-ranging study to evaluate the safety, tolerability and efficacy of CLTX-305 (encaleret) to maintain normalized albumin-corrected blood calcium (cCa) in subjects with hypocalcemia due to ADH1. The study consists of 2 cohorts, 3 periods and a Long-Term Extension (LTE) (Period 1, Period 2, Period 3 and Long-Term Extension [LTE]).

The **primary objectives** of this study are:

- Periods 1 and 2: Evaluate the safety and tolerability of single and multiple doses of CLTX-305 (encaleret) in subjects with ADH1.
- Period 3: Evaluate the safety, tolerability, and efficacy of CLTX-305 (encaleret) in subjects with ADH1 for 24 weeks.
- LTE: Evaluate the long-term (25 months or about 2 years) safety and tolerability of CLTX-305 (encaleret).

The **secondary objectives** of this study are:

Periods 1 and 2:

• Evaluate the effect of CLTX-305 (encaleret) to increase serum intact PTH (iPTH) levels after both single and multiple doses across a dose range in subjects with ADH1.

Periods 1, 2, and 3:

- Evaluate the PD effects of CLTX-305 on blood calcium concentrations.
- Evaluate the PD effects of CLTX-305 (encaleret) on associated measures of calcium. homeostasis including 1,25-(OH)₂ Vitamin D levels and urinary calcium excretion.
- Evaluate the PD effects of CLTX-305 (encaleret) on bone turnover markers including C-telopeptide (CTx) and procollagen type 1 N-propeptide (P1NP).
- Evaluate the PK of both single and multiple ascending doses of CLTX-305 (encaleret) in subjects with ADH1.

LTE:

- Obtain long-term data on efficacy to show durability of CLTX-305 (encaleret) on blood calcium concentrations.
- Evaluate the long-term PD effects of CLTX-305 (encaleret) on associated measures of mineral homeostasis including iPTH, 1,25-(OH)₂ Vitamin D levels and urinary calcium excretion.
- Evaluate the long-term effects of CLTX-305 on bone turnover markers including CTx and P1NP.

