Period 1 (Day1, Day 2, Day 3 and Day 5) and Period 2 (Day 1 if CLTX dose is >	extrapolated to infinity (AUC _{0-inf}) following single- doses.							
180 mg BID and Day 5 regardless of dose received). Even though non- intensive sampling is performed at Period 3 Week 24; PK parameters will be derived at that visit.	- Determination of the steady state PK parameters: C_{max} , trough concentration (C_{trough}), and AUC over the dosing interval AUC _{0-tau} .							

Objectives		Endpoints							
Se	condary								
LT •	 E: Obtain long-term data on efficacy of CLTX-305 (encaleret) on blood calcium concentrations. Evaluate the long-term PD effects of CLTX-305 (encaleret) on associated measures of calcium homeostasis including, iPTH, 1.25-(OH)₂ Vitamin D levels and urinary calcium excretion. Evaluate the long-term PD effects of CLTX-305 (encaleret) on bone turnover markers including CTx and P1NP. 	 LTE: Endpoints measured over time up to 24 months (final visit): Blood calcium - absolute levels and change from baseline in cCa; Urinary calcium clearance (fractional excretion) - absolute levels and change from baseline; Urinary calcium clearance (24-hour total excretion) - absolute levels and change from baseline; Blood levels of iPTH - absolute levels and change from baseline; Blood levels of iPTH - absolute levels and change from baseline; Renal function (eGFR) - absolute levels and change from baseline; Serum levels of 1,25-(OH)₂ Vitamin D -Absolute levels and change from baseline; Blood samples for magnesium, phosphate, creatinine - absolute levels and change from baseline; Time-intervals for urine samples for pH, creatinine and cAMP (time-intervals) - absolute levels and change from baseline; Z4-hours urine samples for pH, magnesium excretion, potassium excretion, creatinine, phosphate excretion, sodium excretion and citrate – absolute levels and change form baseline; Fractional excretion for magnesium and tubular reabsorption of phosphate - absolute levels; Bone resorption markers (blood P1NP) - absolute levels and change from baseline; 							

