- ³ Unscheduled visits: For laboratory evaluation following dose adjustment or assessment or follow-up of an AE, in which clinically indicated procedures will be performed
- ⁴ Document current CLTX-305 (encaleret) dose and calcium dosing regimen, any modifications, and reason for modifications
- ⁵ Outpatient laboratory testing: Blood samples for clinical laboratory panels (Na, Cl, bicarbonate, K, BUN, Cr and including Alb, Ca, Mg, PO₄, iPTH, CTX, and P1NP).
- ⁶ Height measured only at month 24/final visit or ET visit
- ⁷ Vital signs include supine or sitting blood pressure (BP) by automated cuff, heart rate (HR), and respiratory rate.
- ⁸ Safety and Drug Monitoring Labs collected at the NIH CC visits approximately 4 hours after the morning encaleret dose Chemistry (Na, K, Cl, bicarbonate, Glu, BUN, Cr, Alb, total protein, Ca, Mg, PO4, iPTH, 25-OH Vitamin D, CTX, P1NP, Cholesterol, TG, AST, ALT, Tbili, Alk phos, LDH, amylase, lipase, uric acid, CK), Hematology (RBC, Hgb, Hct, RBC indices, WBC, diff), Coagulation (PT/PTT/INR), Research labs (FGF23 and mid-molecule PTH). HIV, viral hepatitis panel should be repeated within 3 months prior to transition to CLTX-305-302/CALIBRATE.
- ⁹ CLTX-305 (encaleret) administered and recorded during the NIH CC visit/in-house days.
- ¹⁰ Outpatient 24-hr urine collection for Ca, Mg, PO4, Cr, Na, K, citrate, pH
- ¹¹ A final follow-up safety telephone call and outpatient labs will occur 30 ± 7 days after the last dose of CLTX-305 (encaleret).
- ¹² If a participant is not able to enter the LTE immediately following Period 3, then participant will be reconsented to and may restart CLTX-305 (encaleret) at the previous therapeutic dose determined in Period 3. Safety and Drug Monitoring Laboratory tests should be done while participant is at the NIH CC.
- ¹³ When participant transitions to CLTX-305-302/CALIBRATE, participant will be asked to return to the NIH CC to complete the ET/EoT visit assessments, return the unused CLTX-305 (encaleret), and complete the screening assessments for the CLTX-305-302/CALIBRATE Phase 3 study. Follow-up labs will not be needed.

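### Serum 1,25-(OH)2 vitamin D is an endpoint of the long-term extension, but no extension panel in this protocol draws it

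*Protocol*

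**What the plan says.** **Objectives and endpoints.** The LTE secondary objective in Protocol 1.1 covers "associated measures of mineral homeostasis including iPTH" and goes on to name 1,25-(OH)2 vitamin D. Protocol 3 repeats the objective and lists serum levels of the analyte among the LTE endpoints. SAP 7.0 has "associated measures of mineral homeostasis including iPTH, 1,25-(OH)₂ Vitamin D levels and urinary calcium excretion", and the LTE list in SAP 9.0 has "Serum levels of 1,25-(OH)₂ Vitamin D -Absolute levels and change from baseline".

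**LTE blood panels.** Protocol Table D defines three:

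- Footnote 8, NIH Clinical Center (NIH CC) visits: "iPTH, 25-OH Vitamin D, CTX, P1NP, Cholesterol, TG, AST, ALT, Tbili, Alk phos, LDH, amylase, lipase, uric acid, CK" among other tests, drawn about 4 hours after the morning dose.
- Footnote 5, outpatient laboratory: electrolytes, renal and mineral tests, ending in "iPTH, CTX, and P1NP".
- Footnote 2, after withdrawal: "blood Cr, Ca, Alb, Mg, iPTH, PO4".

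SAP Table 11 carries the same panels; its footnote 8 again reads "25-OH Vitamin D, CTX, P1NP, Cholesterol, TG".

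**LTE urine.** Table D footnote 11 schedules a 24-hour collection for calcium, magnesium, phosphate, creatinine, sodium, potassium, citrate and pH. It has no timed intervals and no cAMP.

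**Other data source.** Protocol 10.8.3 and SAP 10.14 say that LTE data for these participants may also sit in the CALIBRATE database and will be summarised in this study's report.

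**The concern.** An endpoint named in the objectives of both documents needs a sample. If this protocol's schedule is followed exactly, the CSR addendum that reports the LTE (SAP 12.0) has a 1,25-(OH)2 vitamin D line with nothing from this study to put in it. The Period 3 data on the analyte could then not be extended to show durability.

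The same cross-check finds three lesser mismatches, where the SAP's LTE list and its own tables or derivations disagree. Left alone, they would leave the programmer to decide which text governs.

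**Working it through.** No calculation in the plan is in dispute. The check sets each LTE endpoint against the samples scheduled for it.

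**1. Which panel applies at which visit (Table D).**

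| LTE visits | Panel | 1,25-(OH)2 vitamin D | 25-OH vitamin D |
|---|---|---|---|
| Months 6, 12, 18, 24 (NIH CC) | footnote 8 | no | yes |
| Months 3, 9, 15, 21 (outpatient) | footnote 5 | no | no |
| Follow-up after the last dose | footnotes 2 and 5 | no | no |

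Scheduled visits: 4 + 4 = 8. Visits with the endpoint drawn: 0 of 8. Month 0, for participants restarting after a gap, also uses the footnote 8 panel.

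**2. Where the analyte is drawn.** It appears in Tables E, F, G, H, I and K, all of which cover Periods 1 to 3. The last scheduled samples are at Period 3 Week 24 (Table E), which includes one at 4 hours after the morning dose.

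**3. What could be recovered.** Only NIH CC visits take the footnote 8 panel, so an amendment could add at most 4 of the 8 visits, and fewer for anyone already past some of them. SAP 13.7.1 states that all subjects had completed Week 24, so the LTE may be well advanced. The documents do not give each participant's position.

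**4. Baseline.** SAP 10.1 already supplies one: the last non-missing value before the first Period 2 dose, which also serves Period 3 and the LTE. Calcitriol stops only on Day -1, so this value follows very recent calcitriol. It is also pre-dose, whereas LTE clinic draws are about 4 hours post-dose.

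**5. The smaller items.**

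- *Bone markers.* SAP 9.0 plans LTE change from baseline. This is legible for P1NP and inferred for CTx, because the two lines run together in the available text. SAP Table 6 limits change for both to Period 1. Protocol Tables F and G draw neither marker. Table K draws them only on Period 2 Day 5, so Period 2 schedules no sample before its first dose. CTx and P1NP levels themselves are in footnotes 5 and 8, so absolute values exist at 8 of 8 LTE visits.
- *Timed urine and cAMP.* SAP 9.0 lists interval pH, creatinine and cAMP for the LTE, and SAP 10.1 gives the LTE a timed-interval baseline. Table D collects neither intervals nor cAMP, and a Table 6 footnote already says cAMP is not collected in the LTE. Both protocol endpoint lists still name cAMP.
- *Fractional calcium and magnesium excretion, phosphate reabsorption.* The ingredients are collected at 8 of 8 visits: calcium, magnesium, phosphate and creatinine in 24-hour urine (footnote 11) and in blood (footnotes 5 and 8). SAP 10.3 defines these measures only for the pre-dose sample and within-day intervals, so its formulas do not apply to an LTE collection.

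**The case against.** **CALIBRATE may supply the data.** This is the strongest answer. Protocol 8.2.5 describes assessments there about every 3 months, and SAP 10.14 pools its laboratory data with this study's. A reader might infer that the LTE will have no 1,25-(OH)2 vitamin D value at all; the documents do not support that. They show only that this protocol's panels do not draw it. Equally, nothing in them says that CALIBRATE does.

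**The 25-OH entry could be a misprint.** This is unlikely. The 25-OH form sits in the safety panels of Tables A, B and C, while 1,25-(OH)2 vitamin D is scheduled separately in the sampling tables. The LTE panel matches the safety panels on this point.

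**Table 6 on bone markers looks deliberate.** This stands. Its Period 1 limit fits the absence of a sample before the first Period 2 dose. One might infer that the LTE change analysis should be rebuilt for Cohort 1, since SAP 10.1 lets the Period 1 baseline carry forward. That would override the SAP's analysis table on preference, so SAP 9.0 is the text to correct.

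**Fractional measures do have samples.** This also stands. A reader might take them as impossible to produce, but what is missing is a derivation.

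**All of this is descriptive.** True. Protocol 9.1 plans no hypothesis testing, which limits the weight of the point but does not give the endpoint a sample.

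**Conclusion.** The main point holds for this protocol. One analyte named in the LTE objectives and endpoints of both documents is drawn at 0 of 8 scheduled LTE visits, and at most 4 visits could be recovered by amendment. It should be fixed, because the remedy is cheap and the chance to collect is limited: this study's database closes once the NIH site is activated in CALIBRATE (Protocol 10.8.3).

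The bone-marker, timed-urine and fractional-excretion items are minor wording corrections.

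Confidence is high on the missing assay. It is lower on the bone-marker item, because the SAP 9.0 line is damaged, most Table 6 cell marks are lost, and SAP 10.13, 10.15 and 13.7.3 were not in the text available for this check. The conclusion assumes that CALIBRATE's schedule is unknown. If it includes the assay, the remedy shrinks to a sentence in SAP 10.14. No primary, safety or dosing result depends on any of this.

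**What to change.** **Main change.** By amendment, add 1,25-(OH)2 vitamin D to Table D footnote 8, and to SAP Table 11, for the remaining NIH CC visits (Months 6, 12, 18 and 24 at most). Use the SAP 10.1 baseline. Footnote the output to say that LTE draws are about 4 hours post-dose and that calcitriol stopped only on Day -1, and show the Week 24 4-hour value beside them because its timing matches.

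- If CALIBRATE draws the assay, state that in SAP 10.14.
- If no visits remain and CALIBRATE does not draw it, remove it from the LTE objectives and endpoints (Protocol 1.1 and 3; SAP 7.0 and 9.0) and say so in the CSR addendum.

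**Minor corrections at the same time.**

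- (a) Strike bone-marker change from the SAP 9.0 LTE list and keep absolute levels.
- (b) Remove time-interval urine and cAMP from that list, and take the LTE out of the timed-interval baseline in SAP 10.1. Remove cAMP from the LTE list in Protocol 3. In Protocol 1.1, where one list serves all periods, mark it as not collected in the LTE.
- (c) For LTE fractional calcium and magnesium excretion and phosphate reabsorption, either add to SAP 10.3 a derivation from 24-hour urine and same-visit serum, or remove them (SAP 9.0; Protocol 1.1 and 3 for calcium). A new derivation would take the screening 24-hour urine as baseline and be labelled not comparable with interval values.

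**Cost.** The main change is one assay at existing blood draws, an IRB-approved amendment, and a check against the NIH blood-volume limit, since the documents give no assay volume. Its deletion alternative is wording only. Items (a) to (c) are SAP text plus the protocol endpoint lists, which can go in the same amendment.

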## 1.3.1 Pharmacokinetic, Pharmacodynamic, and Urine Sampling Times

**Table E Non-intensive BID Sampling Days** 

Period 1: Day 4 (BID Dosing)
Period 3: PK/PD sampling days

	Timepoint ± 20 min. (relative to AM dose)
Blood Assays	
PK  samples	-15 min, +30 min, 2, 4, 8, 11, 13 hrs
Intact PTH	-15 min, +30 min*, 2, 4, 8, 11, 13, 17 hrs
Serum bone markers: CTX, P1NP	-15 min, 13 hrs
1, 25-(OH) 2 Vitamin D, cAMP	-15 min, 4, 8, 13,17, 24 hrs 
Ca, PO 4 , Mg, Cr, albumin	-15 min, +30 min*, 2, 4, 8, 11, 13, 17, 24 hrs
K, CK	-15 min, 13 hrs
Urine Assays:	
Timed Interval Urine Collections:	
Ca, Mg, PO 4 , Cr, cAMP, pH	-15 min 0-4 h, 4-8 h, 8-13 h, 13-17 h, 17-24 h
24-Hour urine: Ca, Mg, PO 4 , Cr, Na, K, Citrate, pH	0, 24 hrs (Start collection after first morning void and end 24 hours later)

PK in Period 3 only collected at 24 weeks;

Table F Non-intensive BID Sampling Days - (if CLTX-305 (encaleret) dose is  $\leq$  180 mg BID)

Period 2: Days 1, 2, 3 & 4

	Timepoint ± 20 min. (relative to AM dose)
Blood Assays	
PK samples	-15 min, 2, 4 hrs
Intact PTH	-15 min, +30 min, 2, 4, 8, 11, 13, 17 hrs
1, 25-(OH) 2 Vitamin D	-15 min, 4, 8, hrs
Ca, PO 4 , Mg, Cr, albumin	-15 min, +30 min, 2, 4, 8, 11, 13, 17 hrs
K, CK	-15 min, 13 hrs
Urine Assays:	
Timed Interval Urine Collections: Ca, Mg, PO 4 , Cr, pH	-15 min  , 0-4 h, 4-8 h, 8-13 h, 13-17 h, 17-24 h
24-Hour urine: Ca, Mg, PO 4 , Cr, Na, K, Citrate, pH	0, 24 hrs (Start collection after first morning void and end 24 hours later)

 min urine is done on Period 2 (Day 1) only

<sup>2 24 hour timepoint only collected in Period 3

\* +30 min timepoint only collected in Period 3 at 24 weeks

